6.1. Critical Baseline Assessments

Screening and baseline assessments at Visit 1 or Visit 2 (Week 0) will comprise the following:

- Demographic information including date of birth
- Update medical history
- Cardiovascular medical history/risk factors will be assessed at screening. This assessment must include a review of the subject responses to the cardiovascular assessment questions (See [Appendix 5](#)) and height, weight, blood pressure, medical conditions, and family history of premature cardiovascular disease.
- Therapy history, including review of use of biologics.
- Review of immunogenicity status from MEA112997.
- Physical examination (including nasal exam to check for the presence or absence of nasal polyps.)
- Pulmonary function tests and assessment.
- Assessment of Inclusion/Exclusion criteria. (At Visit 2, will need to review the results of laboratory tests from Visit 1 and the ECG over-read results)
- Asthma Control Questionnaire (ACQ-5). Further details are provided in [Section 6.2.1.3](#)
- Vital signs (further details are provided in [Section 6.3.10.1](#))
- 12-lead ECG (further details are provided in [Section 6.3.10.2](#))
- Blood sampling for the following:
 - Clinical chemistry
 - Clinical chemistry plus lipoproteins at Visit 2 (subject must fast)
 - Haematology
 - Immunogenicity
 - Pregnancy test (all females)
 - HbsAg and hepatitis C antibody
- Parasitic screening (only in countries with a high-risk or in subjects who have visited a country with a high-risk)

6.2. Efficacy

6.2.1. Efficacy Endpoints

- Annualized rate of exacerbations
- Asthma Control Questionnaire score
- FEV₁ measured by clinic spirometry

6.2.1.1. Exacerbations

Exacerbations will be defined as worsening of asthma which requires use of systemic corticosteroids¹ and/or hospitalisation and/or Emergency Department (ED) visits.

¹For all subjects, IV. or oral steroid (e.g., prednisone) for at least 3 days or a single IM CS dose is required. For subjects on maintenance systemic corticosteroids, at least double the existing maintenance dose for at least 3 days is required.

6.2.1.2. Pulmonary Function Testing

Spirometry will be conducted, using the site's own equipment at the visits specified in the Time and Events schedule (Table 2 and Table 3). The spirometer should meet American Thoracic Society standards and produce a printout of all data generated, which should be stored in the subject's notes. The spirometer should be calibrated in accordance with the manufacturer's instructions and a calibration log maintained. Spirometry should be performed within ± 1 hour of the baseline assessment. Subjects should try to withhold short-acting beta-2-agonists (SABAs) for ≥ 6 hours and LABAs for ≥ 12 hours prior to clinic visit, if possible. Assessments to be recorded will include FEV₁ and FVC.

6.2.1.3. Asthma Control Questionnaire-5 (ACQ)

The ACQ-5 is a five-item questionnaire, which has been developed as a measure of subject's asthma control that can be quickly and easily completed [Juniper, 2005]. The questions are designed to be self-completed by the subject. The five questions enquire about the frequency and/or severity of symptoms (nocturnal awakening on waking in the morning, activity limitation, and shortness of breath, wheeze). The response options for all these questions consist of a zero (no impairment/limitation) to six (total impairment/limitation) scale.

The subject should be given a quiet area in which to complete the paper questionnaire. The investigator should ask the subject to complete the questions as accurately as possible. If the subject requests help or clarification with any of the questions, he/she will be asked to re-read the instructions and give the answer that best reflects how he/she felt over the previous week. The subject should be reassured that there are no right or wrong answers. The investigator should not provide the subject with any answer or attempt to interpret any portion of a question. The site-staff will transfer the subject responses on paper into the eCRF.

It is recommended that the ACQ be administered at the same time during each visit. To avoid biasing responses, the subjects should not be told the results of diagnostic tests prior to completing the questionnaire and should be completed before any procedures are performed on the subject to avoid influencing the subject's response. Adequate time should be allowed to complete all items on the ACQ.

6.3. Safety

6.3.1. Safety Endpoints

- Adverse Events, including both systemic (ie, allergic/IgE-mediated and non-allergic) and local site reactions.

NOTE: Hypersensitivity reactions (ie, allergic or IgE-mediated reactions) will be monitored using the diagnostic criteria for anaphylaxis as outlined by the 2006 Joint NIAID/FAAN Second Symposium on Anaphylaxis [[Sampson, 2006](#)] ([Appendix 4](#)). Information will be also collected to assess localised site reactions.

- 12-lead ECG to derive the following endpoints:
 - Mean change from baseline in the QTc(F) (QT interval corrected by Fridericia's method)
 - Mean change from baseline in QTc(B) (QT interval corrected by Bazett's method)
 - Maximum change from baseline for QTc(F) and QTc(B).
- Clinical Laboratory parameters
- Vital signs

6.3.2. Liver chemistry stopping and follow up criteria

Phase III-IV liver chemistry stopping criteria 1-5 are defined below and in [Appendix 3](#):

1. ALT \geq 3xULN and bilirubin \geq 2xULN (>35% direct bilirubin) (or ALT \geq 3xULN and INR>1.5, if INR measured)

NOTE: if serum bilirubin fractionation is not immediately available, withdraw study drug for that subject if ALT \geq 3xULN and bilirubin \geq 2xULN. Serum bilirubin fractionation should be performed if testing is available. If testing is unavailable, **record presence of detectable urinary bilirubin on dipstick**, indicating direct bilirubin elevations and suggesting liver injury.

2. ALT \geq 8xULN.
3. ALT \geq 5xULN but <8 xULN persists for \geq 2 weeks
4. ALT \geq 3xULN if associated with symptoms (new or worsening) believed to be related to hepatitis (such as fatigue, nausea, vomiting, right upper quadrant pain or tenderness, or jaundice) or hypersensitivity (such as fever, rash or eosinophilia).
5. ALT \geq 5xULN but <8 xULN and cannot be monitored weekly for \geq 2 weeks

When any of the liver chemistry stopping criteria 1-5 is met, do the following:

- **Immediately** withdraw investigational product for that subject
- Report the event to GSK **within 24 hours** of learning its occurrence
- Complete the liver event CRF and SAE data collection tool if the event also meets the criteria for an SAE. All events of ALT \geq 3xULN **and** bilirubin \geq 2xULN (>35% direct) (or ALT \geq 3xULN **and** INR>1.5, if INR measured); INR measurement is not required and the threshold value stated will not apply to patients receiving anticoagulants), termed ‘Hy’s Law’, **must be reported as an SAE (excluding studies of hepatic impairment or cirrhosis)**.

NOTE: if serum bilirubin fractionation is not immediately available, withdraw study drug for that subject if ALT \geq 3xULN **and** bilirubin \geq 2xULN. Serum bilirubin fractionation should be performed if testing is available. If testing is unavailable, **record presence of detectable urinary bilirubin on dipstick**, indicating direct bilirubin elevations and suggesting liver injury.

- Complete the liver imaging and/or liver biopsy CRFs if these tests are performed
- Perform liver event follow up assessments, and monitor the subject until liver chemistries resolve, stabilize, or return to baseline values as described below.
- Withdraw the subject from the study after completion of the liver chemistry monitoring (unless further safety follow up is required)
- Do not re-challenge with investigational product.

In addition, for criterion 1:

- Make every reasonable attempt to have subjects return to clinic **within 24 hours** for repeat liver chemistries, liver event follow up assessments (see below), and close monitoring
- A specialist or hepatology consultation is recommended
- Monitor subjects twice weekly until liver chemistries (ALT, AST, alkaline phosphatase, bilirubin) resolve, stabilize or return to within baseline values

For criteria 2, 3, 4 and 5:

- Make every reasonable attempt to have subjects return to clinic **within 24-72 hrs** for repeat liver chemistries and liver event follow up assessments (see below)
- Monitor subjects weekly until liver chemistries (ALT, AST, alkaline phosphatase, bilirubin) resolve, stabilize or return to within baseline values; criterion 5 subjects should be monitored as frequently as possible.

Subjects with ALT \geq 5xULN and <8xULN which exhibit a decrease to ALT \geq 3xULN, but <5xULN and bilirubin <2xULN without hepatitis symptoms or rash, and who can be monitored weekly for 4 weeks:

- Notify the GSK medical monitor within 24 hours of learning of the abnormality to discuss subject safety

- Can continue investigational product
- Must return weekly for repeat liver chemistries (ALT, AST, alkaline phosphatase, bilirubin) until they resolve, stabilize or return to within baseline
- If at any time these subjects meet the liver chemistry stopping criteria, proceed as described above
- If, after 4 weeks of monitoring, ALT <3xULN and bilirubin <2xULN, monitor subjects twice monthly until liver chemistries normalize or return to within baseline values.

For criteria 1-5, make every attempt to carry out the **liver event follow up assessments** described below:

- Viral hepatitis serology including:
 - Hepatitis A IgM antibody;
 - Hepatitis B surface antigen and Hepatitis B Core Antibody (IgM);
 - Hepatitis C RNA;
 - Cytomegalovirus IgM antibody;
 - Epstein-Barr viral capsid antigen IgM antibody (or if unavailable, obtain heterophile antibody or monospot testing);
 - Hepatitis E IgM antibody
- Blood sample for PK analysis, obtained within 4 weeks of last dose. Record the date/time of the PK blood sample draw and the date/time of the last dose of investigational product prior to blood sample draw on the CRF. If the date or time of the last dose is unclear, provide the subject's best approximation. If the date/time of the last dose cannot be approximated OR a PK sample cannot be collected in the time period indicated above, do not obtain a PK sample. Instructions for sample handling and shipping are in the SPM.
- Serum creatine phosphokinase (CPK) and lactate dehydrogenase (LDH).
- Fractionate bilirubin, if total bilirubin $\geq 2xULN$
- Obtain complete blood count with differential to assess eosinophilia
- Record the appearance or worsening of clinical symptoms of hepatitis or hypersensitivity, such as fatigue, nausea, vomiting, right upper quadrant pain or tenderness, fever rash or eosinophilia as relevant on the AE report form
- Record use of concomitant medications, acetaminophen, herbal remedies, other over the counter medications, or putative hepatotoxins, on the concomitant medications report form.
- Record alcohol use on the liver event alcohol intake case report form

The following are required for subjects with ALT ≥ 3 xULN and bilirubin ≥ 2 xULN ($>35\%$ direct) but are optional for other abnormal liver chemistries:

- Anti-nuclear antibody, anti-smooth muscle antibody, and Type 1 anti-liver kidney microsomal antibodies.
- Serum acetaminophen adduct HPLC assay (quantifies potential acetaminophen contribution to liver injury in subjects with definite or likely acetaminophen use in the preceding week.
- Only in those with underlying chronic hepatitis B at study entry (identified by positive hepatitis B surface antigen): quantitative hepatitis B DNA and hepatitis delta antibody. **NOTE:** if hepatitis delta antibody assay cannot be performed, it can be replaced with a PCR of hepatitis D RNA virus (where needed) – as outlined in: <http://www.ncbi.nlm.nih.gov/pmc/articles/PMC1153793/>
- Liver imaging (ultrasound, magnetic resonance, or computerized tomography) to evaluate liver disease.

6.3.3. Adverse Events

Subject will be issued a paper worksheet to record adverse events during the study

The investigator or site staff will be responsible for detecting, documenting and reporting events that meet the definition of an AE or SAE.

6.3.3.1. Definition of an AE

Any untoward medical occurrence in a patient or clinical investigation subject, temporally associated with the use of a medicinal product, whether or not considered related to the medicinal product.

Note: An AE can therefore be any unfavorable and unintended sign (including an abnormal laboratory finding), symptom, or disease (new or exacerbated) temporally associated with the use of a medicinal product. For marketed medicinal products, this also includes failure to produce expected benefits (i.e., lack of efficacy), abuse or misuse.

Events meeting the definition of an AE include:

- Exacerbation of a chronic or intermittent pre-existing condition including either an increase in frequency and/or intensity of the condition
- New conditions detected or diagnosed after study treatment administration even though it may have been present prior to the start of the study
- Signs, symptoms, or the clinical sequelae of a suspected interaction
- Signs, symptoms, or the clinical sequelae of a suspected overdose of either study treatment or a concomitant medication (overdose per se will not be reported as an AE/SAE) unless this is an intentional overdose taken with possible suicidal/self-harming intent. This should be reported regardless of sequelae.

“Lack of efficacy” or “failure of expected pharmacological action” per se will not be reported as an AE or SAE. However, the signs and symptoms and/or clinical sequelae resulting from lack of efficacy will be reported if they fulfill the definition of an AE or SAE.

Events that **do not** meet the definition of an AE include:

- Medical or surgical procedure (e.g., endoscopy, appendectomy); the condition that leads to the procedure is an AE
- Situations where an untoward medical occurrence did not occur (social and/or convenience admission to a hospital)
- Anticipated day-to-day fluctuations of pre-existing disease(s) or condition(s) present or detected at the start of the study that do not worsen
- The disease/disorder being studied, or expected progression, signs, or symptoms of the disease/disorder being studied, unless more severe than expected for the subject’s condition

6.3.3.2. Definition of a SAE

A serious adverse event is any untoward medical occurrence that, at any dose:

- a. Results in death
- b. Is life-threatening

NOTE: The term 'life-threatening' in the definition of 'serious' refers to an event in which the subject was at risk of death at the time of the event. It does not refer to an event, which hypothetically might have caused death, if it were more severe.

- c. Requires hospitalization or prolongation of existing hospitalization

NOTE: In general, hospitalization signifies that the subject has been detained (usually involving at least an overnight stay) at the hospital or emergency ward for observation and/or treatment that would not have been appropriate in the physician’s office or out-patient setting. Complications that occur during hospitalization are AEs. If a complication prolongs hospitalization or fulfills any other serious criteria, the event is serious. When in doubt as to whether “hospitalization” occurred or was necessary, the AE should be considered serious.

Hospitalization for elective treatment of a pre-existing condition that did not worsen from baseline is not considered an AE.

- d. Results in disability/incapacity, or

NOTE: The term disability means a substantial disruption of a person's ability to conduct normal life functions. This definition is not intended to include experiences of relatively minor medical significance such as uncomplicated headache, nausea, vomiting, diarrhea, influenza, and accidental trauma (e.g. sprained ankle) which may interfere or prevent everyday life functions but do not constitute a substantial disruption.

- e. Is a congenital anomaly/birth defect

- f. Medical or scientific judgment should be exercised in deciding whether reporting is appropriate in other situations, such as important medical events that may not be immediately life-threatening or result in death or hospitalization but may jeopardize the subject or may require medical or surgical intervention to prevent one of the other outcomes listed in the above definition. These should also be considered serious. Examples of such events are invasive or malignant cancers, intensive treatment in an emergency room or at home for allergic bronchospasm, blood dyscrasias or convulsions that do not result in hospitalization, or development of drug dependency or drug abuse.

- g. All events of possible drug-induced liver injury with hyperbilirubinaemia defined as ALT \geq 3xULN **and** bilirubin \geq 2xULN (>35% direct) (or ALT \geq 3xULN and INR>1.5, if INR measured) termed 'Hy's Law' events (INR measurement is not required and the threshold value stated will not apply to patients receiving anticoagulants).

NOTE: bilirubin fractionation is performed if testing is available. If testing is unavailable, record presence of detectable urinary bilirubin on dipstick indicating direct bilirubin elevations and suggesting liver injury. If testing is unavailable and a subject meets the criterion of total bilirubin \geq 2xULN, then the event is still reported as an SAE. If INR is obtained, include values on the SAE form. INR elevations >1.5 suggest severe liver injury.

6.3.4. Laboratory and Other Safety Assessment Abnormalities Reported as AEs and SAEs

Any abnormal laboratory test results (haematology, clinical chemistry, or urinalysis) or other safety assessments (e.g., ECGs, radiological scans, vital signs measurements), including those that worsen from baseline, and felt to be clinically significant in the medical and scientific judgement of the investigator are to be recorded as AEs or SAEs.

However, any clinically significant safety assessments that are associated with the underlying disease, unless judged by the investigator to be more severe than expected for the subject's condition, are **not** to be reported as AEs or SAEs.

6.3.5. Cardiovascular Events

Investigators will be required to fill out event specific pages in the eCRF for the following AEs and SAEs:

- Myocardial infarction/unstable angina
- Congestive heart failure
- Arrhythmias
- Valvulopathy
- Pulmonary hypertension
- Cerebrovascular events/stroke and transient ischemic attack
- Peripheral arterial thrombosis
- Deep Venous Thrombosis
- Revascularization

Cardiovascular events information should be recorded on the corresponding eCRF pages within one week of when the AE/SAE(s) are first reported. Please refer to Section [6.3.9](#) for timelines for reporting AE/SAEs.

6.3.6. Death Events

In addition, all deaths will require completion of a specific death data collection page in the eCRF. The death data collection page in the eCRF includes questions regarding cardiovascular (including sudden cardiac death) and non-cardiovascular death.

Death information should be recorded on the death eCRF page within one week of when the death is first reported.

Please refer to Section [6.3.9](#) for timelines for reporting SAEs.

6.3.7. Pregnancy

Any pregnancy that occurs during study participation must be reported using a clinical trial pregnancy form. To ensure subject safety, each pregnancy must be reported to GSK within 2 weeks of learning of its occurrence. The pregnancy must be followed up to determine outcome (including premature termination) and status of mother and child. Pregnancy complications and elective terminations for medical reasons must be reported as an AE or SAE. Spontaneous abortions must be reported as an SAE.

Any SAE occurring in association with a pregnancy, brought to the investigator's attention after the subject has completed the study and considered by the investigator as possibly related to the study treatment, must be promptly reported to GSK.

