4.2. Inclusion Criteria

Specific information regarding warnings, precautions, contraindications, adverse events, and other pertinent information on the GSK investigational product or other study treatment that may impact subject eligibility is provided [GlaxoSmithKline Document Number [CM2003/00010/07](#)].

Deviations from inclusion criteria are not allowed because they can potentially jeopardise the scientific integrity of the study, regulatory acceptability or subject safety. Therefore, adherence to the criteria as specified in the protocol is essential.

Subjects eligible for enrolment in the study must meet all of the following criteria:

1. **Informed Consent:** Prior to commencing any study related activities, subjects must be able and willing to provide written informed consent.
2. **MEA112997 Study Participation:** Received at least 2 doses of double-blind investigational product during the MEA112997 trial.
3. **MEA112997 Treatment Assignment:** If the subject received mepolizumab, they must have had a positive risk: benefit ratio in the opinion of the investigator.
4. **Current Anti-Asthma Therapy:** Asthma is currently being treated with a controller medication and the subject has been on a controller medication for the past 12 weeks. Subjects will be expected to continue controller therapy for the duration of the study.
5. **Male or Eligible Female Subjects:**

To be eligible for entry into the study, **females of childbearing potential** must commit to consistent and correct use of an acceptable method of birth control ([Appendix 2](#)) for the duration of the trial and for 4 months after the last study drug administration.

A serum pregnancy test is required of **all** females. at the initial Screening Visit (Visit 1). In addition, a urine pregnancy test will be performed for **all** females prior to Visit 2, during each scheduled study visit prior to the injection of investigational product, and during the Follow-up Visit.

French subjects: In France, a subject will be eligible for inclusion in this study only if either affiliated to or a beneficiary of a social security category.

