4.5. Withdrawal Criteria

Subjects may be withdrawn from study treatment at anytime by the Investigator if it is considered to be detrimental for them to continue in the study. Reasons for withdrawal can include: an adverse event, lost to follow-up, protocol violation, lack of efficacy, sponsor terminated study, non-compliance, pregnancy, abnormal liver function test, abnormal laboratory results, or for any other reason. Liver chemistry stopping criteria are detailed in Section 6.3.2. In addition, QTc discontinuation criteria are listed below:

- QTc(F)>500 msec or uncorrected QT>600 msec
- Bundle branch block: QTc(F)>530 msec (**Note:** QTc(F)>500 msec for Korean subjects)
- Change from baseline: QTc > 60msec

[Based on average QTc(F) value of triplicate ECGs. If an ECG demonstrates a prolonged QT interval, obtain 2 more ECGs over a brief period, and then use the averaged QTc(F) values of the 3 ECGs to determine whether the patients should be discontinued from the study].

Subjects are free to discontinue participation in the study at anytime. Every effort should be made to have the subject return for a Follow-up visit 4 weeks post last mepolizumab injection. In those instances where the subject specifies the reason for withdrawal of consent, this information will be captured in the eCRF.

A subject should only be designated as lost to follow-up if the site is unable to establish contact with the subject after 3 documented attempts via 2 different methods (phone, text, e-mail, certified letter, etc). These efforts should be documented in the clinic notes at the site.

Subjects may also be withdrawn from this study if mepolizumab becomes commercially available in the respective country, marketing of mepolizumab is no longer being sought in the respective country, or upon decision of the sponsor to discontinue further development of mepolizumab.

The primary reason for withdrawal will be recorded in the eCRF and any data collected up until the point of withdrawal will be used in the data analyses.

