 5. Subject must be in the fasting state. If subject has not fasted, may return the next business day to obtain this sample
 6. Follow-up visit window is \pm 1 week
- * Take additional immunogenicity sample immediately prior to first dose with 100mg vial and prior to the second dose with the 100mg vial. Maximum of 2 additional samples

Table 3 Time and Events Table for Additional Years

Procedures	Treatment subsequent years (repeat 48 week cycle for each subsequent year)													Follow-up 4 weeks post last injection ⁴
	15	16	17	18	19	20	21	22	23	24	25	26	27	
Week of study (± 1 week)	52	56	60	64	68	72	76	80	84	88	92	96	100	
Safety Assessments														
Assess Risk: Benefit ratio	X													
Concomitant Medication	X	X	X	X	X	X	X	X	X	X	X	X	X	
Physical Examination	X													X
Vital Signs	X	X	X	X	X	X	X	X	X	X	X	X	X	X
12-lead ECG						X						X		X
Adverse Events/SAEs	X	X	X	X	X	X	X	X	X	X	X	X	X	X
Laboratory Assessments²														
Haematology						X						X		X
Chemistry plus lipoproteins ³												X		
Chemistry						X								X
Pregnancy Test ¹	U	U	U	U	U	U	U	U	U	U	U	U	U	U
Immunogenicity	*	*	*	*	*	X	*	*	*	*	*	X		X
Efficacy Assessments														
Exacerbation review (worksheet)	X	X	X	X	X	X	X	X	X	X	X	X	X	X
Asthma Control Questionnaire			X			X			X			X		X
Spirometry-						X						X		
IP/eCRF/Worksheets														
Administer IP	X	X	X	X	X	X	X	X	X	X	X	X	X	
Dispense paper diary card	X	X	X	X	X	X	X	X	X	X	X	X	X	
Collect paper diary card	X	X	X	X	X	X	X	X	X	X	X	X	X	X
Phone IVRS	X	X	X	X	X	X	X	X	X	X	X	X	X	
Complete eCRF	X	X	X	X	X	X	X	X	X	X	X	X	X	X

1. Pregnancy test (all females) U = Urine

2. All laboratory tests are to be completed prior to dosing

3. Subject must be in the fasting state. If subject has not fasted, may return the next business day to obtain this sample

4. Follow-up visit window is ± 1 weeks

* Take additional immunogenicity sample immediately prior to first dose with 100mg vial and prior to the second dose with the 100mg vial. Maximum of 2 additional samples

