6.3.8. Time Period and Frequency of Detecting AEs and SAEs

The investigator or site staff is responsible for detecting, documenting and reporting events that meet the definition of an AE or SAE.

AEs will be collected from the start of investigational product (Visit 2) and until the follow up visit (4 weeks after the last injection).

SAEs will be collected over the same time period as stated above for AEs. However, any SAEs assessed **as related** to study participation (e.g., study treatment, protocol-mandated procedures, invasive tests, or change in existing therapy) or related to a GSK concomitant medication, will be recorded from the time a subject consents to participate in the study up to and including any follow up contact. All SAEs will be reported to GSK within 24 hours, as indicated in Section [6.3.9](#).

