11.2. Appendix 2: Acceptable Birth Control

To be eligible for entry into the study, females of childbearing potential must commit to consistent and correct use of an acceptable method of birth control from the time of consent, for the duration of the trial, and for 4 months after the last study drug administration.

- Male partner who is sterile prior to the female subject's entry into the study and is the sole sexual partner for that female subject
- Abstinence from penile-vaginal intercourse
- Implants of levonorgestrel or etonogestrel
- Injectable progestogen
- Oral contraceptive (either combined or progestogen alone)
- Estrogenic vaginal ring
- Percutaneous contraceptive patches
- Any intrauterine device (IUD) with a documented failure rate of less than 1% per year.
- Male condom combined with a vaginal spermicide (foam, gel, film, cream, or suppository)
- Male condom combined with a female diaphragm, either with or without a vaginal spermicide (foam, gel, film, cream, or suppository)

Females of childbearing potential are defined as females with functioning ovaries (i.e., post-menarche, premenopausal women with no documented impairment of oviductal or uterine function that would cause sterility). This category includes females with oligomenorrhea, females who are peri-menopausal, and young females who have begun to menstruate (adolescents). The information on the lack of impairment of oviductal or uterine function that would cause sterility, can come from the site personnel's:

- Review of subject's medical records
- Medical examination of the subject
- Interview with the subject on her medical history.

Females of non-childbearing potential are defined as females with functioning ovaries and with a documented tubal ligation or hysterectomy; or females who are postmenopausal defined as 12 months of spontaneous amenorrhea with an appropriate clinical profile, e.g. age appropriate, >45 years, in the absence of hormone replacement therapy (HRT).

[figure not shown]
In questionable cases a blood sample for follicle stimulating hormone (FSH) and estradiol will be obtained and analyzed to confirm childbearing potential.

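### The duty to notify a pregnancy covers study participation, which in practice ends about 4 weeks after the last dose, while contraception is required for 4 months after it

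*Protocol*

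**What the plan says.** Protocol Section 6.3.7 sets the reporting rule: "Any pregnancy that occurs during study participation must be reported using a clinical trial pregnancy form". Each such pregnancy is to reach the sponsor within 2 weeks of the site learning of it, and is then followed to its outcome, including the condition of mother and child. The section's second paragraph adds a provision for the time after the study: "Any SAE occurring in association with a pregnancy, brought to the investigator's attention after the subject has completed the study" must be reported promptly if the investigator considers it possibly related to study treatment. That provision has no time limit.

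Section 4.5 describes the final contact: "Every effort should be made to have the subject return for a Follow-up visit 4 weeks post last mepolizumab injection". The footnotes to the Time and Events tables allow 1 week either side. Both tables schedule a urine pregnancy test at that visit and none later. Section 6.3.8 ends adverse event collection at the same visit.

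Inclusion criterion 5 in Section 4.2 asks women of childbearing potential to use contraception "for the duration of the trial and for 4 months after the last study drug administration". Appendix 2 repeats the commitment, starting from consent: "for the duration of the trial, and for 4 months after the last study drug administration".

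**The concern.** Both contraception passages list the trial and the 4 months after the last dose as separate periods, so the 4 months cannot simply be read as part of participation. The protocol thus asks women to avoid conceiving during an interval for most of which it does not ask sites to notify a conception.

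A woman who conceives two months after her last injection would be inside the contraception period. Nobody would be required to complete a pregnancy form or follow the pregnancy to its outcome. The primary objective is to describe long-term safety, and pregnancy outcomes not recorded at the time are hard to recover later. Adverse outcomes that do reach the sponsor through the SAE route would also lack a denominator of notified pregnancies from the same interval.

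**Working it through.** The documents give no figure to reproduce. The check is interval arithmetic on the protocol's own periods.

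**Inputs**
- C, the post-dose contraception period: 4 months (Section 4.2, criterion 5; Appendix 2). The protocol does not convert this to days. Assumption: 4 × 365.25/12 = 121.75 days, with a range from 4 × 28 = 112 days to 123 days (four consecutive calendar months, three of 31 days and one of 30).
- F, the time from last injection to the Follow-up visit: 28 days (Section 4.5), or 21 to 35 days with the ±1 week window (footnotes to Tables 2 and 3).
- Assumption: participation ends at the Follow-up visit. This is inferred from the last contact, the last pregnancy test and the end of adverse event collection.

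**Formulas**
- Days without a notification duty: U = C − F
- Share of the contraception period: U / C

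**Results**

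| C (days) | F (days) | U (days) | U / C |
|---|---|---|---|
| 112 | 28 | 84 | 75% |
| 121.75 | 28 | 93.75 | 77% |
| 123 | 28 | 95 | 77% |
| 121.75 | 35 | 86.75 | 71% |
| 121.75 | 21 | 100.75 | 83% |

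Varying both inputs together gives 112 − 35 = 77 days (69%) to 123 − 21 = 102 days (83%).

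**What is already covered in those days**
- A possibly related SAE associated with a pregnancy: reportable under the second paragraph of 6.3.7. This includes a spontaneous abortion, which 6.3.7 makes an SAE, and a birth defect, which Section 6.3.3.2 lists as a seriousness criterion.
- A pregnancy conceived during participation but discovered afterwards: still reportable, because the duty depends on when the pregnancy occurs and the 2-week clock starts when the site learns of it.
- A pregnancy conceived after the Follow-up visit that is uncomplicated, or whose outcome is non-serious or judged unrelated: no provision found. The table in Section 6.3.9 sets only the 2-week clock. The reference to the Study Procedures Manual for post-study procedures names AEs and SAEs, not pregnancies.

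SAP Section 12.7 brings pregnancy into the analysis only through complications and medically indicated terminations recorded as AEs or SAEs. No planned summary depends on the notification window.

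**The case against.** The strongest reply is that the outcomes of most concern are already captured. The SAE clause in 6.3.7 is open-ended, so a possibly related miscarriage or birth defect that reaches the investigator must be reported, even beyond 4 months. This stands and narrows the point considerably. A reader might infer that all pregnancies after the Follow-up visit are lost to safety reporting, and the second paragraph of 6.3.7 rules that out.

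A reader might also infer that the protocol regards women as exposed for 4 months and then ignores that exposure. The text does not say so. Section 4.2 and Appendix 2 state a contraception commitment, with no rationale for its length and no link to reporting. Appendix 2, explaining why male subjects need no contraception, cites the absence of an identified reproductive hazard in preclinical work. A precautionary contraception period can be longer than a reporting period without formal contradiction. What remains is an unexplained mismatch.

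The 4-week end of participation is an inference. That objection is correct, but an undefined term lets sites apply different windows and is itself a reason to state the period.

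The Study Procedures Manual and the consent form were not available, and either might ask for later notification. This cannot be excluded, and no claim is made that the consent form lacks such a line.

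Finally, the amendment log shows an earlier 12-week Follow-up visit. A reader might take the change as proof of error. It is superseded text, and the point rests on the current wording alone.

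**Conclusion.** The point holds in this limited form. As written, 6.3.7 places no duty on sites to notify a pregnancy conceived after the Follow-up visit. With that visit at day 28, this leaves about 84 to 95 days of the 4-month contraception period uncovered (75% to 77%). With C at about 122 days, the visit window gives 87 to 101 days (71% to 83%). The affected pregnancies are those that are uncomplicated, or whose outcomes are non-serious or judged unrelated to treatment.

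These percentages measure calendar time, not pregnancies missed. The protocol caps enrolment at 608 subjects but gives neither the number of women of childbearing potential nor a pregnancy rate, so no expected count can be derived. The number is probably small. The result depends on the day-count assumption for 4 months and on reading participation as ending at the Follow-up visit. It does not affect any planned analysis. It is a gap in safety capture that is cheap to close in a study whose primary purpose is safety.

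**What to change.** Reconcile Section 6.3.7 with Section 4.2 and Appendix 2. State explicitly how long after the last dose a pregnancy is to be notified, and align that period with the contraception period already stated, for any pregnancy the site learns of. The same sentence should make clear that follow-up to outcome applies to these pregnancies, and should remove the dependence on an undefined term. At the existing Follow-up visit, remind women to tell the site if they become pregnant within that period.

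Reporting stays passive. No visit or test is added, and the contraception and dosing rules are unchanged. The cost is a sentence in the protocol, a reminder at a visit that already takes place, and a small number of additional reports to follow up after study exit.
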